6.9 Efficacy

To evaluate efficacy of camostat by effect on COVID-19 related clinical improvement.

Time Frame: Days 1-28

Time to worst point on the scale or deterioration of two points or more (from randomisation) on a 9-point category ordinal scale.

9-point category ordinal scale:

0. Uninfected, no clinical or virological evidence of infection
1. Ambulatory, no limitation of activities
2. Ambulatory, limitation of activities
3. Hospitalised – mild disease, no oxygen therapy
4. Hospitalised – mild disease, oxygen by mask or nasal prongs
5. Hospitalised – severe disease, non-invasive ventilation or high-flow oxygen
6. Hospitalised – severe disease, intubation and mechanical ventilation
7. Hospitalised – severe disease, ventilation and additional organ support e.g. vasopressors, renal replacement therapy (RRT), extracorporeal membrane oxygenation (ECMO)
8. Death

Table 10 Ordinal Scale.

Efficacy population

Patient Number	Randomised Arm (Treatment or Control Arm)	Day 1 Scale	Worst Point on Scale	Deteriorated by more than 2 points (yes/no)	Time to worst point (Days)

Table 11: Summary Table for Secondary Endpoint Data.

Efficacy population

	All	Treatment arm	Control arm

Number of community patients admitted to hospital due to COVID-19			
Total number of patients			
Proportion of patients per arm			
Supplementary oxygen-free days at 28 days			
Number of patients			
Proportion of patients per arm			
Ventilator-free days at 28 days			
Number of patients			
Proportion of patients per arm			

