4 OBJECTIVES AND ENDPOINTS

Primary Objective and Endpoint	
Objective	Endpoint
To further assess the safety and toxicity profile of camostat, to support integration into a Phase III trial.	Causality and severity of each adverse event (AE) to camostat.
Secondary Objectives and Endpoints	
Objective	Endpoint
To confirm that the PK profile aligns with the established PK profile for the active metabolite of camostat, 4-(4-guanidinobenzoyloxy) phenyl acetic acid (GBPA).	Confirm PK parameters of GBPA as assessed by population estimates from population PK analysis (popPK).
To assess the ability of camostat to reduce the requirement for COVID-19 related hospital admission in community patients with SARS-CoV-2 infection.	Rate of COVID-19 related hospital admission in community patients with SARS-CoV-2 infection.
To evaluate the requirement for supplementary oxygen (non-invasive or mechanical invasive) in patients who have received camostat as treatment for SARS-CoV-2 infection.	Supplementary oxygen-free days at 28 days (from randomisation).
To evaluate the requirement for ventilation in patients who have received camostat as treatment for SARS-CoV-2 infection.	Ventilator-free days at 28 days (from randomisation).
To evaluate efficacy of camostat by effect on COVID-19 related clinical improvement.	
Time Frame: Days 1-28
 
Time to worst point on the scale or deterioration of two points or more (from randomisation) on a 9-point category ordinal scale.
 
9-point category ordinal scale:
 
 0. Uninfected, no clinical or virological evidence of infection 1. Ambulatory, no limitation of activities 2. Ambulatory, limitation of activities 3. Hospitalised – mild disease, no oxygen therapy 4. Hospitalised – mild disease, oxygen by mask or nasal prongs 5. Hospitalised – severe disease, non-invasive ventilation or high-flow oxygen 6. Hospitalised – severe disease, intubation and mechanical ventilation 7. Hospitalised – severe disease, ventilation and additional organ support – vasopressors, renal replacement therapy (RRT), extracorporeal membrane oxygenation (ECMO) 8. Death

Research Objectives and Endpoints	
Objective	Endpoint
[REDACTED]	[REDACTED] [REDACTED] [REDACTED]
[REDACTED]	[REDACTED] [REDACTED] [REDACTED] [REDACTED] [REDACTED]
[REDACTED]	[REDACTED] [REDACTED]

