5 TRIAL DESIGN

5.1 Summary of trial design

A randomised, multicentre, prospective, open label clinical trial.

The trial aims to recruit up to 100 patients.

The Trial Management Group (TMG) described in Section 5.2.1, will perform ongoing review of the emerging data to inform adaptive decision making during the trial. Please see Section 5.2.1. for further details.

During the trial, patient enrichment strategies may be implemented e.g. adapting the inclusion criteria to include emerging co-morbidities, neutrophil/lymphocyte ratio, other blood biomarkers, age, in order to support trial endpoints and feasibility. All clinical data will be reviewed on a regular basis by the Sponsor and TMG to inform this adaptive design, collaborating with the Trial Steering Committee (TSC) as per Section 5.2.2.

If review of the data (during any part of the trial) results in proposed substantial amendments, these will be submitted to the Medicines and Healthcare products Regulatory Agency (MHRA) and Research Ethics Committee (REC) for an opinion.

Patients may be identified in/through various settings e.g. GP practices, primary care COVID hubs, community-based testing centre, drive through testing facilities, advertisement, secondary care or equivalent clinical settings. Further detail on how patients will be recruited is provided in Section 9.1. It is likely that testing availability and strategy will change in the UK and the trial will respond by engaging with testing sites as applicable, to support recruitment. Before any new sites are opened for this trial, risk assessments will be performed to ensure that the protocol and procedures can be performed safely for both patients and site staff.

If a patient consents to the trial and fulfils eligibility criteria, they will be randomised to either the treatment arm or the control arm. Patients in the treatment arm will be asked to take camostat for 14 consecutive days and patients in the control arm will be asked to continue with best supportive care.

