5.3 Intervention

5.3.1 Randomisation

Patients will be randomised by the site staff using an interactive web response system (IWRS). Confirmation of the patient randomisation will be sent to the Investigator, site clinical trial team and Sponsor following enrolment and randomisation of the patient. The patient will be notified of their allocated group by the clinical research team.

Randomisation will be to one of two arms and a randomisation ratio of 1:1 will be applied:

- **Treatment arm:** patient to receive treatment with camostat 200 mg qds for 14 days.
- **Control arm:** patients will receive best supportive care.

⁶ The PSRB acts as an independent body across the portfolio of studies at the CR UK Centre for Drug Development (CDD). The PSRB charter mandates that the members are independent from CR UK, CDD and can act as an independent body.

All patients randomised will receive a trial pack to include [REDACTED]

[REDACTED] instructions for use as well as a diary card to record these readings and, if randomised to camostat, to document their compliance with dosing. If patients wish to do so, they can use the Medidata patient application ('app') in addition to the diary card. The trial pack will include an app instruction and consent document. The research team or courier will deliver the appropriate trial pack.

For patients recruited while in hospital, all assessments will be performed and camostat will be given by the hospital staff (if the patient is randomised to camostat). Patients will receive a trial pack to include [REDACTED] instructions for use only on discharge. If patients wish to do so, they can use the Medidata patient application ('app') in addition to the diary card and app instructions and consent form can be provided.

Patients randomised to the treatment arm will also be offered best supportive care in managing the disease.

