5.3.3 Dose interruptions/ Withdrawal criteria

- If a clinically significant abnormality is identified, camostat will be interrupted and blood samples will be taken for analysis.
- If abnormal results are identified, the patient will be referred to the GP for further assessment where local protocols will be followed.
- If required, patient hospital attendance with a suspected adverse event will trigger SAE reporting and the Investigator and Sponsor will make a causality assessment.
- Possible, Probably and Highly Probable causality assessment to camostat will result in treatment withdrawal.
- If the patient recovers symptomatically and biochemical analysis returns to the normal range, re-starting camostat can be considered by the Investigator and Sponsor to include an assessment whether the patient is likely to be past the initial stage of infection. For patients where it is deemed appropriate to re-start the patient, a maximum of 48 hrs treatment interruption will be allowable.

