8.3.2 Days 7 and 14: Home visit consultation with clinical professional

The intention is that for community patients **home visits** occur on Days 7 and 14 to take research bloods [REDACTED]. However, this requirement may change if patients are able to provide samples by visiting the site but only in accordance with government and clinical advice. For those patients in hospital, Day 7 and 14 visits can occur in hospital face to face. If the Sponsor and site decide that sampling is not required, this will be communicated to the patient. The Days 7 and 14 video (phone) calls will still go ahead as planned regardless of sampling.

- [REDACTED]
- Biochemical and haematological investigations to include:
 - Haematology – Hb, WBC, neutrophils, lymphocytes, and platelets.
 - Biochemistry – sodium, potassium, magnesium, adjusted calcium, phosphate, urea, creatinine, total protein, albumin, bilirubin, ALP, ALT, AST, clotting-PT, APTT, GGT, troponin, D-dimer.

- Raised parameters will be managed as per usual Trust clinical management. If results indicate that the patient should be admitted, the clinical research team will contact the patient and arrange for them to come into hospital for further assessment. For dose interruption/withdrawal criteria, see Section 5.3.3

- [REDACTED]
- Blood sample for pharmacokinetics (PK) assessment (patient will be asked to consent to PK sampling within main study ICD and that this will also be document within the patient's medical notes)

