12.5 Reporting Procedures for Serious Adverse Events

For eligible patients, SAE collection and monitoring (as per risk assessed monitoring plan) will commence at the time the patient gives their written/verbal consent (whichever is the earlier) to participate in the trial and will continue for 28 days from Day 1.

In addition to the SAE reporting criteria in Section 12.1.3,

During the trial period (Days 1-28):

- All hospitalisations as per the definition stated in Section 12.1.3 (regardless of causality) will be followed up until resolution, discharge or death.
- Patients who are hospitalised will also be followed up, up to 28 days after they are discharged.

Following the trial period, up to the Day 28, only SAEs related to camostat are reportable. These will be followed up until resolution, discharge or death.

Should an Investigator become aware of any IMP-related SAEs after this period, these must also be reported to the CDD within the expedited timelines.

All SAEs regardless of causality must be reported to the Pharmacovigilance Department within 24 hours of becoming aware of the event. SAEs should be documented on an SAE report form, using the completion guidelines provided. SAE report forms should be emailed to the Pharmacovigilance Department mailbox: [REDACTED] The following information must be provided as a minimum:

- Patient identifiers including patient trial number and initials, age or date of birth and gender,
- SAE term, onset date and causality assessment
- A description of the SAEs
- Dose and duration of the treatment with the medicine
- The batch number of the medicine
- Any other medications being taken at the same time including non-prescriptive medicines, herbal remedies and contraceptives
- Any other health conditions the patient has or may have

Follow-up of SAEs by the Pharmacovigilance Department will continue until the events resolve or stabilise. The Pharmacovigilance Department will make requests for further information on SAEs to the Investigators at regular intervals. Requested follow-up information should be reported to the

Pharmacovigilance Department in a timely manner and as soon as possible after receipt of the follow-up request or within 24 hours of becoming aware of new/updated information.

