8 TABLES LISTINGS AND FIGURES

8.1 LISTINGS:

Completed or Discontinued patients

Treatment compliance End of monitoring period (Control arm)

End of study

Protocol deviations

Patients excluded from efficacy analysis

Screening failures

EnrolmentDemographic and Baseline Data

Demographics

Randomisation

Medical history

Risk factors

COVID-19 symptoms

Influenza or COVID-19 Vaccination

Concomitant medications

Medical procedures

Compliance and/or Drug Concentration Data

Treatment compliance Efficacy Response Data

9-point ordinal scale for clinical improvement

COVID-19/Camostat related hospitalisation details

Oxygen therapy and ventilation

Hospitalisation follow up

Safety Data

Adverse Events (by subject)

Adverse Events by SOC

Pregnancy test

Laboratory results

Imaging

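### The only planned by-arm admission outcome rests on open-label attribution to COVID-19; add an all-cause admission count by arm beside it

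*SAP*

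**What the plan says.** Protocol section 5.1 describes the trial as "A randomised, multicentre, prospective, open label clinical trial", and section 5.3.1 adds: "The patient will be notified of their allocated group by the clinical research team". The control arm receives best supportive care without placebo.

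The admission endpoint in Protocol section 4 is "Rate of COVID-19 related hospital admission in community patients with SARS-CoV-2 infection". RAP Table 11 (section 6.9) implements it as "Number of community patients admitted to hospital due to COVID-19", by arm, in the efficacy population. The registry outcome in RAP section 7.4 uses the same cause-specific count. The intention-to-treat analysis in section 11.1 of the SAP appendix, planned if the data allow, is also confined to COVID-19 related admissions.

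On attribution, Protocol section 5.3.3 says that "patient hospital attendance with a suspected adverse event will trigger SAE reporting and the Investigator and Sponsor will make a causality assessment". RAP section 6.7 defines a COVID-19 related adverse event by a tick box, and a treatment-related one by a separate causality grade.

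On data, Protocol section 12.5 says: "All hospitalisations as per the definition stated in Section 12.1.3 (regardless of causality) will be followed up until resolution, discharge or death". RAP section 8.1 plans a listing headed "COVID-19/Camostat related hospitalisation details" and another for hospitalisation follow-up, for which no cause limit is stated.

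**The concern.** Whether an admission is due to COVID-19 is a judgement. No section defines it for an admission, names who makes it, or provides review blind to allocation. In an open-label trial with an untreated control, that judgement need not work alike in the two arms.

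The documents show how the two explanations can overlap. Protocol section 8.1 lists shortness of breath and diarrhoea among COVID-19 symptoms. Section 12.6 lists dyspnoea (with shock or anaphylactoid symptoms) and gastrointestinal events among the camostat events of interest. Section 12.2 asks assessors to consider whether an event is already known with the drug. A camostat patient admitted with such a picture can be attributed to the drug; a control patient with the same picture cannot.

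At stake is the direction of a secondary estimate that Protocol section 13.1 says is reported to inform future trials. If attribution differs by arm, the estimate leans towards camostat, and the planned tables offer no all-cause admission figure by arm to set beside it.

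**Working it through.** **The plan's own figure.** The documents give no expected rate or precision for admissions. The only precision statement (Protocol section 13.2) concerns the recruitment rate: 50%, SE 3.5%, 95% CI 43% to 57%. It reproduces if 100 recruited patients imply 100/0.50 = 200 approached: SE = sqrt(0.5 × 0.5/200) = 3.54%, and 50% ± 1.96 × 3.54% = 43.1% to 56.9%. It says nothing about admissions.

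**Step 1: does any planned output give the all-cause count?**

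| Output | What it gives | Why it is not the count |
|---|---|---|
| RAP Table 11; RAP 7.4 | Community patients admitted, by arm | COVID-19 admissions only |
| SAP appendix 11.1, intention-to-treat | Main secondary outcomes | COVID-19 admissions only; conditional on the data |
| RAP Table 10 | Arm, Day 1 level and worst ordinal level per patient; levels 3-7 mean hospitalised, whatever the cause | Per-patient listing; efficacy population; scale assessed daily to Day 14, then only on Days 21 and 28 |
| RAP Table 6 | Patients with at least one treatment-emergent SAE, by arm | Mixes admissions with other serious events; not limited to community patients |
| RAP 8.1 listings | Hospitalisation details and follow-up | Not by-arm counts; one is limited by cause, the other has no stated scope |
| RAP 7.3 | All-cause mortality by arm | Deaths only |

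None gives the number of community patients with any admission, by arm.

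**Step 2: size of one recoded admission.** Inputs: 1:1 allocation and up to 50 per arm (Protocol synopsis). One camostat admission moved out of the endpoint changes that arm's proportion by 1/50 = 2 percentage points. Table 11 is limited to community patients in the efficacy population, so the denominator may be smaller; at an illustrative 40 it would be 1/40 = 2.5 points.

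**Step 3: range under stated assumptions.** Assume the same true all-cause risk r in both arms, all admissions otherwise counted as COVID-19, and a share q of camostat admissions labelled as not due to COVID-19. The spurious difference is r(1 − q) − r = −qr, and the risk ratio is 1 − q.

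| r | q = 10% | q = 25% | q = 50% |
|---|---|---|---|
| 4% | −0.4 | −1.0 | −2.0 |
| 10% | −1.0 | −2.5 | −5.0 |
| 20% | −2.0 | −5.0 | −10.0 |
| Risk ratio | 0.90 | 0.75 | 0.50 |

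(differences in percentage points)

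In whole patients, with 5/50 admitted in each arm:
- One recoded: 4/50 v 5/50 = −2 points, SE = sqrt(0.08 × 0.92/50 + 0.10 × 0.90/50) = 5.7 points.
- Two recoded: 3/50 v 5/50 = −4 points, SE = sqrt(0.06 × 0.94/50 + 0.10 × 0.90/50) = 5.4 points.
- All-cause row in either case: 5/50 v 5/50 = 0, SE = sqrt(2 × 0.10 × 0.90/50) = 6.0 points.

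**Step 4: does the population matter?** Under Protocol section 5.3.3, causality to camostat of possible or stronger leads to treatment withdrawal. RAP section 5.1 requires five days of camostat for the efficacy population, but keeps controls who leave early because of an endpoint such as hospitalisation. A camostat patient withdrawn before five days therefore drops out of Table 11. An all-cause row in the efficacy population alone would still depend partly on attribution.

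**The case against.** The strongest reply is that recoded admissions stay visible. With at most 100 patients, a reader of Table 10 can count by arm those who moved from level 2 or below to level 3 or above, and no level asks for a cause. An admission put down to camostat would appear in the listing of COVID-19 and camostat-related hospitalisations. As an SAE, it would also enter the camostat-related events reported for the primary outcome. Oxygen-free and ventilator-free days carry no cause attribution. All of this stands, and it rules out saying that the reader has no attribution-free information. What remains missing is the direct by-arm count.

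The second reply is that the mechanism is inferred. Section 5.3.3 concerns causality to camostat, not whether an admission is due to COVID-19. The two labels are separate items, so an admission may carry both and stay in the endpoint. An admission unrelated to either is possible in both arms. This also stands.

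A reader might further take Protocol section 8.3.2 as evidence of a one-way effect: "If results indicate that the patient should be admitted, the clinical research team will contact the patient and arrange for them to come into hospital". That provision applies to both arms. It shows that staff who know the allocation can influence the decision to admit, not that they do so in one direction.

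**Conclusion.** The point holds as a cheap improvement. Every planned by-arm admission analysis depends on attribution to COVID-19 in an open-label trial, without described adjudication, although hospitalisations are followed regardless of cause. Only one arm has a drug to which an admission can be attributed.

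The firm size is 2 points per recoded admission if the denominator is 50. The −4 point example rests on an assumed 5/50 in each arm and two recoded admissions; neither figure comes from the documents, and the shift is within one standard error. The endpoint is secondary and descriptive, with no significance testing planned in Protocol section 13.1.

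A reader might infer that the admission result will be biased towards camostat, or that drug-attributed admissions vanish from the report. The documents support neither. Nothing forces relabelling, and such admissions would surface in other outputs.

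**What to change.** 1. In RAP Table 11 and the RAP section 7.4 outcome, add by arm the number and proportion of community-recruited patients with any hospital admission on Days 1-28, regardless of cause. Give it for all randomised patients as well as for the efficacy population.
2. Split the count into COVID-19-related, camostat-related and other, allowing an admission to be both COVID-19- and camostat-related.
3. State the admission definition. The SAE criterion in Protocol section 12.1.3 covers stays of more than 24 hours and exempts planned ones. The alternative is any admission found in the record review of section 8.3.4; that section names oxygen use, imaging and death as its purposes, so admissions would need to be recorded explicitly.
4. Keep the COVID-19-related row and present the all-cause figure beside it as the attribution-free check.
5. Make the RAP section 8.1 hospitalisation listing cover all hospitalisations.

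The cost is a few table rows and a wider listing filter, using data largely collected already. Unrelated admissions will slightly dilute the all-cause figure, and it does not remove the influence of known allocation on the decision to admit.

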6.10 General data conventions

Data will be grouped according to the assigned treatment arm, as specified in the study protocol. Patients who deviate from the assigned treatment arm will be clearly described in the CSR with regards to their treatment modification and if applicable in the list of protocol deviations (Section 5.2).

Continuous variables will be summarised and presented with summary statistics.

Categorical variables will be summarised in frequency tables. Percentages in the summary tables will be rounded and may therefore not always add up to exactly 100%.

The convention in Rave is that an unknown day resolves to 1st of the month and an unknown month resolves to January. Dates may be ordered by this, however CRUK do not perform calculations on unknown dates.

Durations of AEs: the start date of an AE is considered as Day 1 of the event and should be included in all duration calculations (i.e. if an AE starts and stops on same day, the duration should be reported as one day).

- For unrelated AEs, those with missing or partially completed end dates will not be excluded from analysis and the duration of the AE will remain as unknown.
- For related AEs, prior to final data lock, an end date will be either i) confirmed AE end date or ii) stabilisation of AE. If lost to follow-up then the AE would stay as not recovered/not resolved. In both these cases duration would not be calculated.

Time to onset of AEs from IMP administration: the time to onset should be calculated from the date of the first administration of IMP in the trial (e.g. Day 1). Onset time will be calculated as 0 if the AE occurs on the same day as the dose.

